# STUDY PROTOCOL

# 1. STUDY INFORMATION

Title	Effectiveness of bivalent Covid-19 booster vaccines in the
	Nordic countries
Protocol version identifier	1
Date of latest version of	3 October 2023
protocol	
EU PAS Register number	[N/A]
Medicinal products	Comirnaty Original/Omicron BA.1 (BNT162b2)
	Comirnaty Original/Omicron BA.4-5 (BNT162b2)
	Comirnaty Original monovalent (BNT162b2)
	Spikevax Original/Omicron BA.1 (mRNA-1273 [/Moderna covid-
	19 vaccine])
	Spikevax Original/Omicron BA.4-5 (mRNA-1273 [/Moderna covid-
	19 vaccine])
	Spikevax Original monovalent (mRNA-1273 [/Moderna covid-19
	vaccine])
	Vaxzevria (ChAdOx1-S [/AZD1222])
Marketing authorization	Pfizer/BioNTech
holder(s)	Moderna
	AstraZeneca
Research question and	The aim of this project is to evaluate the comparative effectiveness
objectives	of the bivalent boosters in preventing severe Covid-19 outcomes
	and all-cause mortality among individuals aged 50 years or older
	with 1 year of follow-up.
Country(-ies) of study	Denmark, Norway, Finland, and Sweden
Authors	[name]; [name]

# 2. MARKETING AUTHORIZATION HOLDER(S)

Not applicable.

#### 4. ABSTRACT

Rationale and background: The larger Nordic countries of Denmark, Finland, Norway, and Sweden, provide a unique setting for the study of Covid-19 vaccination effectiveness. The ubiquitous nationwide demography- and health registers, which includes SARS-CoV-2 immunization and surveillance registers, allows for very large study cohorts with near real-time data availability. Available evidence suggests that bivalent booster vaccinations during autumn 2022 provided additional protection against Covid-19 hospitalisations while protection against any SARS-CoV-2 infection is more modest. The bivalent booster vaccines were offered to the general public as a fourth dose during autumn 2022 as well as an additional booster for immunocompromised individuals. However, current studies only provide insight on effectiveness in follow-up periods that do not extend beyond 2-6 months and on the Omicron subvariants prevailing during the study period.

**Research question and objectives**: The aim of this project is to evaluate the comparative effectiveness of the bivalent boosters in preventing severe Covid-19 outcomes and all-cause mortality among individuals aged 50 years or older with up to 1 year of follow-up.

## **Primary objectives:**

- 1. To provide estimates of VE against severe Covid-19 outcomes at day 365 after immunisation with a BA.1 or BA.4-5 bivalent booster as a fourth dose, comparing a) the BA.1 and BA.4-5 bivalent booster against not having received a fourth dose and b) between the BA.1 and BA.4-5 bivalent and the original monovalent booster.
- 2. To provide estimates of waning of VE against severe Covid-19 outcomes as the three-monthly relative reduction in vaccine effectiveness until day 365 after immunisation with a BA.1 or BA.4-5 bivalent booster as a fourth dose, comparing a) the BA.1 and BA.4-5 bivalent booster against not having received a fourth dose and b) between the BA.1 and BA.4-5 bivalent and the original monovalent booster.
- 3. To provide estimates of VE against all-cause mortality at 3, 6, and 9 months post discharge for COVID-19 hospitalisation, comparing a) individuals who received BA.1 and BA.4-5 bivalent boosters as fourth dose against individuals not having received a fourth dose and b) individuals who received the BA.1, BA.4-5 bivalent or original monovalent boosters.

### Secondary objectives:

4. To provide VE estimates at day 90/180/365 (pending data distribution) after immunisation with a bivalent booster among immunocompromised individuals.

- 5. To provide VE estimates at day 365 after immunisation with a bivalent booster among females and males, and 50-69-year-olds and 70+-year-olds.
- 6. To provide VE estimates at day 365 after immunisation with a bivalent booster according to time since a previous infection.
- 7. To provide VE estimates at day 365 after immunisation with a bivalent booster according to time between-dose intervals (for both the primary course and the booster doses).
- 8. To provide VE estimates at day 365 after immunisation with a bivalent booster according to the vaccine brand received as fourth dose.

**Study design**: Nationwide register-based cohort analyses in Denmark, Finland, Norway, and Sweden during the study period from 27 December 2020 until latest available date in 2023 at time of analyses (e.g., 30 September 2023).

Population: Source cohorts will consist of all individuals who are known residents in the four Nordic countries and have received at least three vaccine doses (i.e., a primary two-dose vaccination course and one booster) with the AZD1222 (Vaxzevria, Oxford-AstraZeneca; as part of the primary vaccination only), BNT162b2, and/or mRNA-1273 vaccines between 27 December 2020 and latest available date in 2023. The main study cohort will consist of individuals who are at least 50 years of age in Denmark, 60 in Finland, 65 in Norway, and 50 in Sweden and eligible fourth dose recipients will include those receiving a fourth dose after (including on this day) 1 September 2022 in Denmark, 18 July 2022 in Finland, and 1 July 2022 in Norway and Sweden. Secondary study cohorts will consist of 1) main study cohort individuals hospitalized for Covid-19 and 2) immunocompromised individuals aged ≥18 years.

**Variables**: The outcomes of interest will be Covid-19 hospitalisation, Covid-19 mortality and all-cause mortality for the third primary objective. Covariates will be variables of demography, comorbidity, and previous Covid-19 infection and vaccination.

**Data sources**: Nationwide demography- and healthcare registers within each participating country.

**Study size**: We expect to include at least 3.37 million individuals who have received 4 doses of Covid-19 vaccines (representing a primary course followed by two booster doses) across the 4 Nordic countries. The statistical power of our proposed study is reflected in the VE results from our recent Nordic study on the VE of the bivalent boosters (based on data up until April 2023).(1)

**Data analysis:** Using target trial emulation, we will compare bivalent booster dose recipients head-to-head and with unboosted individuals as well as between booster recipients in matched survival

analysis that provides comparative effectiveness estimates while taking into account a range of covariates.

**Milestones:** Study start: 1 August 2023; study planning meeting: 16 August 2023; final first version of study protocol: 5 September 2023; study report: 1 December 2023; manuscript draft: 1 April 2024.

## **5. AMENDMENTS AND UPDATES**

Number	Date	Section	Amendment or update	Reason

## **6. MILESTONES**

Milestones	Planned dates
Study start	1 August 2023
Study planning meeting	16 August 2023
Study Protocol submission (posted on EU-PAS register when approved by EMA).	5 September 2023
Registration in the EU-PAS Register	5 September 2023
Study Report submission (posted on EU-PAS register when approved by EMA).	1 December 2023
Manuscript(s) ready for submission.	1 April 2024

#### 7. RATIONALE AND BACKGROUND

The emergence of the SARS-CoV-2 Omicron variant in late 2021 quickly raised concerns about the effectiveness of the original monovalent Covid-19 vaccines. Bivalent booster vaccinations, which incorporated components from both the ancestral strain and the Omicron variant, were developed to improve protection against the new predominant variant. Subsequently, bivalent boosters were introduced in many countries, including the Nordic countries during autumn 2022 as a 4th dose to the general adult population (and as any additional booster for immunocompromised individuals) and results from a number of studies evaluating the effectiveness of bivalent booster vaccinations in different populations and settings are now available.

The protection afforded by the bivalent boosters against SARS-CoV-2 infection appears to be modest.(2-4) In the United States, Link-Gelles and colleagues investigated the comparative effectiveness of bivalent mRNA booster doses against symptomatic SARS-CoV-2 infection in individuals who had previously received monovalent vaccines only.(2) The study found that a bivalent mRNA booster dose provided additional protection against symptomatic XBB/XBB.1.5 infection for at least the first three months after vaccination in individuals who had previously received 2-4 monovalent vaccine doses. Vaccine effectiveness was 52% against symptomatic BA.5 infection and 48% against symptomatic XBB/XBB.1.5 infection in persons aged 18-49 years. A cohort study conducted in the Netherlands by Huiberts and colleagues, assessed the comparative effectiveness of bivalent BA.1 vaccination against self-reported Omicron SARS-CoV-2 infection.(3) The study involved 32,542 participants who had previously received primary and one or two monovalent booster Covid-19 vaccinations. The results showed 31% effectiveness in 18-59-year-olds and 14% effectiveness in 60-85-year-olds, indicating that a bivalent booster provided little additional benefit in preventing SARS-CoV-2 infection. A study in Qatar evaluated the comparative effectiveness of the bivalent mRNA-1273.214 vaccine against SARS-CoV-2 infection in individuals aged 12 and older.(4) The study reported a modest protection of 24.7% against infection with the bivalent vaccine in a period dominated by the Omicron XBB subvariants. The protection was 16.4% among persons with no prior infection and 35.3% among persons with prior infection.

In contrast to infection, the bivalent boosters appear to protect well against severe Covid-19 outcomes such as hospitalisation and death.(5–11) In an early US study, a bivalent booster dose offered significant additional protection against Covid-19-associated hospitalisations among adults aged 65 and older.(6) When compared to unvaccinated individuals, the vaccine effectiveness was 84%, and when compared to individuals who had received two or more doses of monovalent mRNA vaccines it was 73%. In Israel, the comparative effectiveness of a bivalent booster dose in reducing

hospitalisations and deaths due to Covid-19 in individuals aged 65 years or older was evaluated in a study cohort comprising 569,519 participants, including 134,215 (24%) who were given a bivalent booster.(9) The results showed that those who received the bivalent mRNA booster had a lower rate of Covid-19 related hospitalisations compared to those who did not receive the booster corresponding to an effectiveness of 72%. These findings emphasise the importance of bivalent mRNA booster vaccinations in populations at high risk of severe Covid-19. In a larger cohort of individuals aged 12 years or older from North Carolina, a bivalent booster (1.07 million vaccine recipients) was more effective than a monovalent booster (292,659 individuals), with a vaccine effectiveness of 61.8% against severe infection resulting in hospitalisation or death, compared to 24.9% for the monovalent booster. (7,8) Evidence of waning was observed after a peak at 4 weeks, although less pronounced for the bivalent booster. The Moderna and Pfizer-BioNTech bivalent boosters showed similar effectiveness. In our recent Nordic study, we examined the comparative vaccine effectiveness of the bivalent mRNA-booster vaccines in 3.37 million individuals aged 50 or older.(1) The study found that receipt of a bivalent BA.4-5 booster as a fourth dose was associated with a country-combined VE against Covid-19 hospitalisation of 67.8%, while the corresponding VE for bivalent BA.1 boosters was 65.8%. In addition, we observed no significant difference between BA.4-5 and BA.1 boosters when directly compared.

In summary, the available evidence suggest that bivalent booster vaccinations can provide additional protection against severe Covid-19 events and, to a lesser extent, infections. However, current studies only provide insight on effectiveness in follow-up periods that do not extend beyond 2-6 months and on the Omicron subvariants prevailing during the study period.

## 8. RESEARCH QUESTION AND OBJECTIVES

The aim of this project is to evaluate the comparative effectiveness of the bivalent boosters in preventing severe Covid-19 outcomes and all-cause mortality among individuals aged 50 years or older with 1-year of follow-up.

## **Primary objectives:**

1. To provide estimates of VE against severe Covid-19 outcomes at day 365 after immunisation with a BA.1 or BA.4-5 bivalent booster as a fourth dose, comparing a) the BA.1 and BA.4-5 bivalent booster against not having received a fourth dose and b) between the BA.1 and BA.4-5 bivalent and the original monovalent booster.

- 2. To provide estimates of waning of VE against severe Covid-19 outcomes as the three-monthly relative reduction in vaccine effectiveness until day 365 after immunisation with a BA.1 or BA.4-5 bivalent booster as a fourth dose, comparing a) the BA.1 and BA.4-5 bivalent booster against not having received a fourth dose and b) between the BA.1 and BA.4-5 bivalent and the original monovalent booster.
- 3. To provide estimates of VE against all-cause mortality at 3, 6, and 9 months post discharge for COVID-19 hospitalisation, comparing a) individuals who received BA.1 and BA.4-5 bivalent boosters as fourth dose against individuals not having received a fourth dose and b) individuals who received the BA.1, BA.4-5 bivalent, or original monovalent boosters.

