of interest		protocol effect.
Statistical analysis	Kaplan-Meier estimator to obtain cumulative incidence for each treatment strategy during follow-up. Compare cumulative incidence across treatment strategies by risk ratios (to obtain VE) and risk differences.  Person-time since baseline will be stratified consecutive in three-months periods with the Kaplan-Meier estimator to estimate third-monthly changes in VEs; these VEs will contribute to meta-regression estimating comparative waning.	Same as for the target trial except observational analogs of perprotocol.

Subgroup analyses by sex (female/male), age ( ≥70 years), time between vaccine dose (between primary</th 	course and 3rd dose and 3rd and 4th dose; for	
general population target trial), and vaccine brand	
(Pfizer-BioNTech/Moderna).	

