We will follow individuals from day 8 after the index date (to ensure full immunisation among booster recipients) up until the day of an outcome event, 365 days has passed since the index date (i.e., allowing up to 357 days of follow-up since day 8), receipt of additional booster, death, emigration, or end of the study period, whichever occurs first.

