## Statistical analysis

We will use logistic regression to estimate the propensity score of receiving a specific booster dose given covariates as predictors. We will match (without replacements) on age, calendar time of last mutual vaccine dose (i.e., third or fourth dose), and the propensity score (with a calliper width of 0.01).

Cumulative incidences will be estimated by the Kaplan-Meier estimator, and from these we will calculate the comparative VE as 1 – risk ratio at day 365. The corresponding 95% CI will be calculated using the delta method. Country-specific estimates will be combined by random-effects meta-analyses implemented using the *mixmeta* package in R.

Comparative waning will be estimated using meta-regression.(39) First, we will estimate the VEs (in the specific comparison being evaluated) in each consecutive three-months period (day 8-90, day 91-180, 181-270, and 271-365) by stratification on time since booster vaccination. Second, the resulting estimates will be analysed using meta-regression to provide a ratio of VEs per three-month intervals as a measure of waning.

Subgroup analyses will be conducted according to sex, age groups ( $</\ge70$  years), time since last SARS-CoV-2 infection (<6, 6-12, >12 months), time between primary course and first booster ( $</\ge12$  months), time between first and second booster ( $</\ge12$  months), and bivalent booster brand (Pfizer-BioNTech and Moderna).

*All-cause mortality (objective #3)* 

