In secondary cohorts of individuals aged  $\geq 18$  years with presumed immunocompromised conditions, we will evaluate the effectiveness of the bivalent boosters received as the  $\geq 4$ th dose. We will utilize the same analytical matched approach as in the main analysis described above. Dependent on the data distribution, time of VE assessment may be day 180 or day 365 since booster vaccination. Similarly, dependent on data availability, we will further subgroup bivalent booster recipients according to booster received as fourth, fifth, or  $\geq$ sixth dose, and we will endeavour to assess similar subgroups as in the main cohort subgroup analyses including waning VE analysis. The VE estimates will be indirectly compared with the VE estimates from the main cohort analysis while stressing the limitations of such indirect comparisons.

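### VE at day 365 is a cumulative day 8-365 measure that is not labelled as such, and the immunocompromised cohort may be compared with the main cohort at a different horizon

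*Protocol*

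**What the plan says.** - **Objective (Section 8).** Primary objective 1 is "To provide estimates of VE against severe Covid-19 outcomes at day 365 after immunisation". Objectives 5-8 also ask for VE at day 365. None of them uses the word cumulative.
- **Estimator (Section 9.7, Statistical analysis; target-trial table in Section 9.1).** Kaplan-Meier cumulative incidences are estimated, and "from these we will calculate the comparative VE as 1 – risk ratio at day 365". The target-trial table agrees: "Compare cumulative incidence across treatment strategies by risk ratios (to obtain VE) and risk differences". Follow-up starts on day 8 and stops at the latest when "365 days has passed since the index date (i.e., allowing up to 357 days of follow-up since day 8".
- **Waning (objective 2; Section 9.7).** VE is first estimated "in each consecutive three-months period (day 8-90, day 91-180, 181-270, and 271-365) by stratification on time since booster vaccination". These estimates then enter a meta-regression that yields a ratio of VEs per three months.
- **Outputs (Section 12).** Waning VE is listed among the planned figures. The example main table has columns for the risk difference and comparative VE only.
- **Immunocompromised cohort (objective 4).** Section 8 allows day 90, 180 or 365, the target-trial table ends follow-up at 180 days, and Section 9.7 allows day 180 or day 365. Section 9.7 then states: "The VE estimates will be indirectly compared with the VE estimates from the main cohort analysis".

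**The concern.** Section 7 gives the reason for the study: "current studies only provide insight on effectiveness in follow-up periods that do not extend beyond 2-6 months". A risk ratio over days 8-365 includes all of that already studied period. On its own it does not show how much protection is left after month 6. A reader who sets a VE at day 365 beside the 67.8% from the earlier Nordic study, which rests on follow-up to day 90, may take the difference as a year of waning. Because the new figure also contains the first 90 days, that difference would understate waning.

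Objective 2 addresses waning but delivers a ratio, and a ratio does not give the level of protection late in the year.

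The same property affects objective 4 more directly. When effectiveness changes over time, cumulative VE depends on where it is read. Two cohorts read at different days can therefore differ although their effectiveness is the same in every window.

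**Working it through.** **The protocol's own figures.** It states no VE at day 365, no VE for days 271-365 and no incidence by period. The one figure to reproduce is the length of follow-up: 365 − 8 = 357 days, which agrees with Section 9.7.

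**Formula.** Let h_k be the reference-arm hazard accumulated in window k and VE_k the effectiveness in that window. Summing over windows up to day t,

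VE_cum(t) = 1 − [1 − exp(−Σ h_k(1 − VE_k))] / [1 − exp(−Σ h_k)].

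For rare outcomes this is close to Σ w_k VE_k, where w_k is window k's share of the reference-arm events up to day t.

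**Inputs.**
- Windows: the four in Section 9.7.
- Window VEs: 67, 45, 25 and 10%. The first is close to the 67.8% (BA.4-5) and 65.8% (BA.1) against hospitalisation in Section 7. The other three are assumptions.
- Event shares: assumed, either even (25/25/25/25) or front-loaded (50/25/15/10).

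**Results (4 vs 3 dose contrast).**

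| | Even | Front-loaded |
|---|---|---|
| Cumulative to day 365 | (0.67 + 0.45 + 0.25 + 0.10)/4 = 0.3675 | 0.335 + 0.1125 + 0.0375 + 0.010 = 0.495 |
| Cumulative to day 180 | (0.67 + 0.45)/2 = 0.560 | (0.335 + 0.1125)/0.75 = 0.597 |
| Difference due to horizon alone | 0.1925 | 0.102 |
| VE in days 271-365 | 0.10 | 0.10 |

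**Sensitivity.** This uses the exact formula, an assumed one-year reference risk of 1%, and VE falling linearly from 67.8% to 10% (67.8, 48.5, 29.3, 10). Cumulative VE at day 365 by assumed risk shares:
- flat incidence: 37.7%
- 45/30/15/10: 50.3%
- 60/25/10/5: 56.1%
- back-loaded 15/15/30/40: 30.1%

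A geometric decline with flat incidence gives 31.9%. A reference risk of 5% moves these values by about half a point. Under the linear decline, reaching 50% needs about 80% of the reference-arm risk to fall in days 8-180. The cumulative value exceeds the last-window 10% in every case, but the size of the excess depends on the assumptions.

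**How much data reach the last window.** With the tentative end date of 30 September 2023 (Section 9.1), only index dates up to 30 September 2022 can reach day 365, and only those up to 2 January 2023 can reach day 271.

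**The case against.** The estimator is stated openly in two places, and a risk ratio at a fixed horizon is a standard target-trial estimand. Section 9.9 describes the analyses as evaluations of vaccination strategies, which suits a cumulative measure. Extending follow-up to one year meets the gap as Section 7 words it. Waning is itself a primary objective, the day 271-365 VE is already planned, and the table in Section 12 is only an example. All of this stands. It makes the first part a matter of labelling and reporting and not an error of calculation.

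A reader might infer that the headline VE will be dominated by the first winter and will read about 50% when protection at one year is about 10%. The documents do not support that. The autumn 2022 roll-out makes front-loaded risk plausible, but no incidence by period is given and the 10% endpoint is assumed. The illustration also does not carry over to the booster-vs-booster contrasts: Section 7 reports no significant difference between BA.4-5 and BA.1.

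A reader might also infer that durability should be judged on days 271-365 alone. Section 9.9 warns that near day 365 the 4 vs 3 comparison is dominated by people who never take a fourth dose, with possible healthy vaccinee bias. Section 9.8 foresees heavy censoring. The last window is the sparsest and the most exposed to this selection.

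On the immunocompromised comparison, Section 9.7 promises to stress the limits of indirect comparison and Section 9.9 calls it not ideal. Those cautions concern the matched populations and the differing vaccination schedules. Neither mentions horizon, so they do not answer the point. Section 9.8 lets the main cohort move to day 180 or 270 if data are thin, but it does not tie that choice to the day used for the immunocompromised.

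**Conclusion.** The point holds in two parts.

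First, objective 1's VE at day 365 is cumulative over days 8-365 and is not labelled so. If VE wanes, it will exceed late-year VE. In the illustration it is about 37% or 49.5%, against 10% in days 271-365. These figures rest on assumed window VEs and event shares, apply to the 4 vs 3 dose contrast only, and do not predict the result.

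Second, following the plan can produce a difference between the immunocompromised and main cohorts through horizon alone. With identical effectiveness it is about 10 points with front-loaded events (59.7% vs 49.5%) and about 19 points with even events (56% vs 36.75%). This is the firmer defect, because the plan permits the mismatch and no caveat covers it. It disappears if both cohorts are read at the same day.

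**What to change.** 1. In Section 9.7 (immunocompromised), compare the two cohorts only at the same horizon, by also reading the main-cohort Kaplan-Meier estimates at the day used for the immunocompromised. Reconcile the 180-day end of follow-up in the target-trial table with the day-365 option in Sections 8 and 9.7.
2. In objectives 1 and 5-8 and in the results table, call the measure cumulative VE, days 8-365 (or to whichever day is finally used).
3. In the main table, report the already planned window-specific VEs, including days 271-365, with CIs beside the cumulative VE. Add a note pointing to the selection and sparse follow-up described in Sections 9.8 and 9.9, and do not rest a durability conclusion on the last window alone.

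The cost is wording, one extra reading of an existing curve and one or more table columns. The late-window figure will be less precise and probably less favourable than the cumulative one.
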